This is a single-center, prospective cohort study of subjects undergoing clinically indicated PET/CT MPI, with documented coronary artery disease or an intermediate to high pretest likelihood of coronary artery disease. Following the clinical study, the research study is explained to the subjects. Consenting subjects will return on another day (next calendar day or later) for a repeat stress study with Lexercise or a repeat Lexiscan stress PET. Approximately 50 subjects (not more than 16 patients with normal Rubidium-82 or N-13 ammonia PETMPI, 10 healthy volunteers and 24 patients with reversible perfusion defects) will be enrolled in this study. After successful screening and enrollment, 13 random subjects (8 normal and 5 ischemic) will return for repeat Lexiscan PET, and 37 subjects will return for a Lexercise PET/CT MPI. Lexiscan PET will be performed per standard protocol. For Lexercise, a symptom limited exercise treadmill study with Lexiscan injection at peak exercise is performed. Rubidium-82 or N-13 ammonia will be injected and PET/CT images will be obtained in a list mode acquisition. Images will then be unlisted and myocardial blood flow computed.

Number of Subjects Planned

Approximately 50 subjects will be enrolled into the study.

Main Selection Criteria

Subjects will be eligible if they meet all of the following inclusion criteria and none of the exclusion criteria:

Inclusion criteria:

- Age > 18 years
- Clinically indicated Rubidium-82 or N-13 ammonia PET study
- Ten healthy volunteers recruited using web based advertisements.
- Known coronary artery disease (prior percutaneous coronary intervention, prior coronary artery bypass surgery or Q wave MI on ECG) or intermediate to high pretest likelihood of CAD
- Able to exercise on a treadmill
- Able and willing to provide informed consent to participate in the study

Exclusion criteria:

- Contraindications to exercise stress testing such as
 - unstable angina
 - known severe left main coronary artery stenosis
 - severe or uncontrolled heart failure
 - uncontrolled atrial or ventricular arrhythmias
 - symptomatic hypotension or severe hypertension (systolic blood pressure < 90 or > 200 mmHg, respectively)
 - > 1st degree atrioventricular block in the absence of a functioning pacemaker.
- Contraindications to Lexiscan use such
 - Allergy or intolerance to aminophylline or regadenoson

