 - Known severe or oxygen dependent bronchoconstrictive or bronchospastic lung disease [e.g., asthma, wheezing, chronic obstructive pulmonary disease (COPD), etc.].
 - Sick sinus syndrome
 - History of heart transplantation.
 - Dialysis
 - Subject requires emergent cardiac medical intervention or catheterization after the clinical study.
 - Documented myocardial infarction (MI) ≤ 30 days prior to enrollment.
 - History of percutaneous coronary intervention (PCI) ≤ 4 weeks prior to enrollment.

- History of coronary artery bypass graft (CABG) \leq 8 weeks prior to enrollment.
- Severe LV dysfunction, with ejection fraction of $< 30\%$
- Serious non-cardiac medical illness (e.g., disseminated malignancy, severe neurological dysfunction at time of baseline PET study) or a social situation which will preclude research study participation
- History of seizure disorder

Discontinuation criteria:

Subjects should be discontinued for the following discontinuation criteria

- Subject does not fulfill inclusion or exclusion criteria
- Subject experiences a serious or intolerable adverse event
- In the Investigator's opinion, the subject is non-compliant with the protocol requirements (protocol violation)
- Subject's health would be jeopardized by continued participation
- Subject wishes to withdraw consent

Lexiscan will not be administered to patients with clinical or EKG evidence on ischemia during exercise treadmill testing. Clinical or EKG abnormalities during treadmill testing that would preclude administration of Lexiscan are listed below:

- a) Clinical
 - a. Severe chest pain
 - b. Severe lightheadedness or dizziness,
 - c. Severe shortness of breath
 - d. Exercise induced hypotension ($> 10\text{mm Hg}$ decrease in systolic blood pressure)
 - e. Exercise induced hypertension (systolic blood pressure $> 210\text{ mm Hg}$)
- b) ECG changes
 - a. Significant ST segment depression ($\geq 2\text{ mm}$)
 - b. Significant ST segment elevation ($\geq 1\text{ mm}$)
 - c. Sustained ventricular or atrial tachycardia,
 - d. Exercise induced heart block

Statistical Plan:

The overall aim of this pilot study of 50 patients is to assess the tolerability, safety, diagnostic accuracy and image quality between Lexiscan with symptom limited exercise compared to Lexiscan alone.

Aim 1. For this aim, we will compare the reported side effect profile for Lexercise to Lexiscan PET, using a Pearson Chi square test. A P-value of <0.05 will be considered significant.

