Aim 2: For this aim, we will compare objective measures of image quality including signal to noise ratio using dynamic Rubidium-82 or N-13 ammonia images, the frequency of misregistration between PET and CT, the frequency of presumed motion artifact and bowel radiotracer activity. These measures will be compared using a student's t-test or a Pearson Chi square test, as appropriate. A P-value of <0.05 will be considered significant.

Aim 3: For this aim, we seek to compare measures of semi quantitative relative perfusion, absolute perfusion and LVEF using the Lexiscan alone compared to Lexercise PET. Firstly, we will compare semi-quantitative defect size, severity and reversibility between the Lexercise and Lexiscan PET studies. Based on the results of one prior study using N-13 ammonia and comparing dipyridamole versus treadmill exercise², a sample size of 24 subjects with reversible defects should be adequate to identify if significant differences exist between Lexercise and Lexiscan PET protocols. Next, we will compare the differences in regional rest and peak stress myocardial blood flow and coronary flow reserve in the defect territory compared to normal territory between the Lexercise and Lexiscan protocols. Finally, we will study the changes in LVEF from rest to peak stress in Lexercise versus Lexiscan PET studies in the normal and ischemic subjects.

[figure not shown]
I. BACKGROUND:

Myocardial perfusion imaging (MPI) with positron emission tomography (PET) is more accurate than single photon emission computed tomography (SPECT)³, enables non-invasive quantitation of absolute myocardial blood flow (MBF), and is particularly helpful in the obese individuals and those that are unable to exercise.³ Presently PETMPI is indicated only for subjects that are unable to exercise⁴,

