	Exercise Stress	Dipyridamole Stress	p Value	Correlation	Significance of Correlation
Summed stress score	9.1 ± 5.7	6.9 ± 5.9	<0.01	0.80	<0.001
Summed rest score	3.4 ± 3.3	3.2 ± 2.8	NS	0.79	<0.001
Summed difference score	5.8 ± 4.7	3.7 ± 4.6	<0.02	0.61	0.001
LV defect size (stress) (%)	19.3 ± 11.5	13.8 ± 13.6	<0.02	0.62	0.001
LV defect size (rest) (%)	8.1 ± 9.4	6.4 ± 6.5	NS	0.57	0.003

Values are mean ± SD.

LV = left ventricle; PET = positron emission tomography.

Myocardial count density of N-13 ammonia was significantly greater with dipyridamole compared to exercise stress. Successful performance of exercise ammonia required coordination between the cyclotron team and the imaging team. The authors concluded that treadmill exercise produces larger and more severe perfusion defects than dipyridamole and may reflect true ischemia.

III. STUDY METHODS

This is a single-center, prospective cohort study of subjects undergoing clinically indicated PET/CT MPI, with documented coronary artery disease or an intermediate to high pretest likelihood of coronary artery disease based on age gender and symptoms as described in the ACC/AHA/ASNC appropriate use criteria for cardiac radionuclide imaging.¹² Following completion of the clinical study, the research study is explained to the subjects. Consenting subjects will return on another day for a repeat stress study with Lexercise or a repeat Lexiscan stress PET. Approximately 50 subjects (not more than 16 patients with normal Rubidium-82 PETMPI and 34 with reversible perfusion defects) will be enrolled in this study. After successful screening and enrollment, 13 random subjects (8 normal and 5 ischemic) will return for repeat Lexiscan PET, and 34 subjects will return for a Lexercise PET/CT MPI, on the next calendar day or within 2 weeks of the clinical Rubidium-82 or N-13 ammonia PET study.

SUBJECT SELECTION

Main Selection Criteria

Subjects will be eligible if they meet all of the following inclusion criteria and none of the exclusion criteria:

Inclusion criteria:

- Age > 18 years
- Clinically indicated Rubidium-82 or N-13 ammonia PET study
- Ten healthy volunteers recruited using web based advertisements.

- Known coronary artery disease (prior percutaneous coronary intervention, prior coronary artery bypass surgery or Q wave MI on ECG) or intermediate to high pretest likelihood of CAD
- Able to exercise on a treadmill
- Able and willing to provide informed consent to participate in the study

Exclusion criteria:

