- Hospital in-patients with request for pharmacologic stress: Attending physicians will be asked if they felt comfortable introducing the study to their subjects that they schedule for in-patient pharmacologic stress myocardial perfusion study verbally during their visit. If the physician introduces the study verbally, the subject will be asked if they would like to speak with a coordinator after the visit. If they would like to speak with someone, the coordinator will be notified and they will explain the study to the subject and go over the inclusion and exclusion criteria for the study. If they are interested in participating in the study an appointment will be made for their first visit.
- Special attention will be paid to enroll women and minorities in the study.
- Ten healthy volunteers will be recruited for this study using web based advertisements. They will all undergo Lexiscan (regadenoson) followed by Lexercise protocol (exercise + regadenoson) on a separate day.

b) Procedures for obtaining informed consent (including timing of the consent process)

For subjects interested in speaking to a study staff, Study PI, will go over the inclusion and exclusion criteria and will describe the study and procedures to the potential subject over the phone or in person. If the subject qualifies and is interested he/she is encouraged to discuss the study with his/her primary care physician or family members. Upon arrival for the study, the subject will be given a copy of the consent form to read. After the subject has finished reading the consent form, one of the physician investigators will describe the study in detail and answer any questions or concerns

the subject might have. If the subject agrees to participate in the study they will be asked to provide his/her written informed consent. Subjects will be given a copy of the signed consent form for their records. The investigator will inform the subject that they have the alternative not to participate in the study and can withdraw their consent at any point during the study.

The subjects will be given as much as 2 weeks to consider participation in the trial. Pregnant women and minors are excluded from this trial. Subjects that are determined by the physician to be unable to consent due to their physical or mental condition will not be enrolled in this trial.

V. STUDY PROCEDURES

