The patient will have 1-2 study visits and healthy volunteers will have 2-3 study visits. Study visit 1 is the same for patients and healthy volunteers.

a. Study visit 1

- a. The subjects that are interested in the study will meet with [name] and go over the consent form and details of study participation.
- b. This screening visit will take about 1 hour. The research study team will ask the subject questions about medical history, medications, and prior hospitalizations to make sure that the subject qualifies for this study. Blood pressure, heart and breathing rates, temperature, and height and weight will be measured. Pregnancy is not allowed due to the unknown risks radioactivity may have on the mother or the unborn baby from the beginning of the study period through the end of the study. A blood pregnancy test will be performed on the day of the PET scan in women with child bearing potential.

Patients:

a. Study visit 2

The study visits 1 and 2 can be conducted on the same day. Study visit 2 is for the performance of the Lexercise stress Rubidium-82 or N-13 ammonia PET study. This will be scheduled at least the next calendar day or within 2 weeks of the clinical Rubidium-82 or N-13 ammonia PET study. While we aim to conduct the research scan within 2 weeks of the clinical scan, if there is a scanner malfunction or patient schedule conflict, we would like to extend the time frame for enrollment to 4 weeks.

Approximately 20 cc of blood will be drawn following completion of the Rubidium-82 or N-13 ammonia imaging study and evaluated for biochemical markers of ischemia.

b. Study Visit 3

Study visit 3 is for the performance of the Lexercise stress Rubidium-82 or N-13 ammonia PET study. This will be scheduled at least the next calendar day or within 2 weeks of the clinical Rubidium-82 or N-13 ammonia PET study. Approximately 20 cc of blood will be drawn following completion of the Rubidium-82 or N-13 ammonia imaging study and evaluated for biochemical markers of ischemia. A part of this blood sample (10 cc) will be sent to the laboratory of [name] for the isolation of microRNAs involved in angiogenesis and vascular inflammation. This blood sample will be stored for future analysis.

Healthy volunteers:

a. Study visit 2

The study visits 1 and 2 can be conducted on the same day. Study visit 2 is for the performance of the rest and regadenoson stress Rubidium-82 or N-13 ammonia PET study. No blood drawing will be performed during this visit.

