- Sub diaphragmatic activity (liver heart ratios)
- Defect contrast
- Signal to noise ratio and
- Dynamic image evaluability will be assessed

VI. BIOSTATISTICAL ANALYSIS

The overall aim of this pilot study of 50 patients is to assess the tolerability, safety, diagnostic accuracy and image quality between Lexiscan with symptom limited exercise compared to Lexiscan alone.

Aim 1. For this aim, we will compare the reported side effect profile for Lexercise to Lexiscan PET, using a Pearson Chi square test. A P-value of <0.05 will be considered significant.

Aim 2: For this aim, we will compare objective measures of image quality including signal to noise ratio using dynamic Rubidium-82 images or N-13 ammonia, the frequency of misregistration between PET and CT, the frequency of presumed motion artifact and bowel radiotracer activity. These measures will be compared using a student's t-test or a Pearson Chi square test, as appropriate. A P-value of <0.05 will be considered significant.

Aim 3: For this aim, we seek to compare measures of semi quantitative relative perfusion, absolute perfusion and LVEF using the Lexiscan alone compared to Lexercise PET. Firstly, we will compare semi-quantitative defect size, severity and reversibility between the Lexercise and Lexiscan PET studies. Based on the results of one prior study using N-13 ammonia and comparing dipyridamole versus treadmill exercise², a sample size of 35 subjects with reversible defects should be adequate to identify if significant differences exist between Lexercise and Lexiscan PET protocols. Next, we will study the changes in LVEF from rest to peak stress in Lexercise versus Lexiscan PET studies in the normal and ischemic subjects. Finally, we will compare regional rest and peak stress myocardial blood flow and coronary flow reserve between Lexercise and Lexiscan PET studies.

VII. RISKS AND DISCOMFORT

Time: Participation in this trial entails an exercise vasodilator stress Rubidium-82 PET or N-13 ammonia scan. The total time spent for the study procedures is approximately 1 hour.

Intravenous line insertion: Possible side effects intravenous line insertion are pain, bruising, or infection where the needle entered the skin. Some people faint or get dizzy during insertion of the intravenous line.

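### The Aim 3 sample size is 24 in the Synopsis and 35 in Section VI, cites the wrong study, and the Synopsis allocation leaves at most 19 reversible-defect subjects with both scans

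*Combined protocol and SAP*

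**What the plan says.** **Sizing sentence.** Synopsis, Statistical Plan, Aim 3: "a sample size of 24 subjects with reversible defects should be adequate to identify if significant differences exist between Lexercise and Lexiscan PET protocols". Section VI, Aim 3: "a sample size of 35 subjects with reversible defects should be adequate". Both sentences describe a prior N-13 ammonia study and carry citation 2.

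**Enrolment and allocation.** The Synopsis (Design and Methodology) enrols at most 16 patients with normal scans, 10 healthy volunteers and 24 patients with reversible defects. It then states that "13 random subjects (8 normal and 5 ischemic) will return for repeat Lexiscan PET, and 37 subjects will return for a Lexercise PET/CT MPI". Section III instead enrols "not more than 16 patients with normal Rubidium-82 PETMPI and 34 with reversible perfusion defects", with no volunteers in the count, and continues: "13 random subjects (8 normal and 5 ischemic) will return for repeat Lexiscan PET, and 34 subjects will return for a Lexercise PET/CT MPI". Section IV says of the 10 volunteers: "They will all undergo Lexiscan (regadenoson) followed by Lexercise protocol".

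**Visits.** For patients, Section V states "Study visit 2 is for the performance of the Lexercise stress Rubidium-82 or N-13 ammonia PET study", then describes visit 3 as a Lexercise scan too. It gives patients one or two visits in total and schedules no repeat-Lexiscan visit.

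**Withholding rule.** Synopsis, Discontinuation criteria: "Lexiscan will not be administered to patients with clinical or EKG evidence on ischemia during exercise treadmill testing".

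**Analysis.** A significance threshold of 0.05 is attached to Aims 1 and 2 only. Aim 3 has no stated test, alpha, sidedness, power or main defect measure.

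**The concern.** The sizing sentence is the only justification of sample size in the document, and it exists in two current forms that disagree. A reader cannot tell which number governs.

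The Aim 3 defect comparison is within subject: a Lexercise scan is set against the same person's Lexiscan scan. What matters is therefore the number of reversible-defect subjects with both scans. Under the one allocation whose counts close, that number is below the smaller of the two stated sizes.

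The printed citation does not help. By the protocol's own account, reference 2 found no significant difference in defect size, so it cannot support a claim that such a difference would be detected.

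If the trial finds no difference in defect size or severity, a reader relying on the plan would take that as the result of an adequately sized study. The counts do not support that reading.

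**Working it through.** **1. Counts.**

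- Synopsis enrolment: 16 + 10 + 24 = 50. Synopsis return groups: 13 + 37 = 50. The return groups add up to total enrolment, and subjects return for one scan type or the other, so the groups are disjoint.
- Reversible-defect subjects left for Lexercise: 24 − 5 = 19.
- Cross-check from the Lexercise side: 37 − 10 volunteers − (16 − 8) normals = 19.
- Section III enrolment: 16 + 34 = 50. Its return groups give 13 + 34 = 47, so three subjects are unaccounted for. If its groups are also disjoint, 34 − 5 = 29 have both scans. Even the 34 enrolled is below Section VI's 35.

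Nineteen is a ceiling, because any subject from whom Lexiscan is withheld after exercise loses the pair. The document gives no rate for this. The limit applies to the defect and defect-territory flow comparisons. The LVEF comparison also uses normal subjects.

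**2. Can 24 or 35 be reproduced?** Not from stated inputs, since Aim 3 gives no power, test or target difference. My assumptions are a paired t-test, two-sided alpha 0.05, and effects from Table 3 of the N-13 study (under Rationale for specific aim 3): exercise versus dipyridamole, 26 patients.

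SD of the paired difference = √(s₁² + s₂² − 2·r·s₁·s₂).

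- Summed stress score (SSS): difference 9.1 − 6.9 = 2.2; SD = √(5.7² + 5.9² − 2·0.80·5.7·5.9) = 3.67; d = 2.2/3.67 = 0.599.
- Summed difference score (SDS): difference 5.8 − 3.7 = 2.1; SD = √(4.7² + 4.6² − 2·0.61·4.7·4.6) = 4.11; d = 0.511.
- Stress defect size (% LV): difference 19.3 − 13.8 = 5.5; SD = √(11.5² + 13.6² − 2·0.62·11.5·13.6) = 11.10; d = 0.495.

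Check: with t = d·√26 on 25 degrees of freedom, p = 0.005, 0.015 and 0.018. The table prints <0.01, <0.02 and <0.02, so the derived SDs are consistent with it.

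**3. Power** (noncentral t with n − 1 degrees of freedom, noncentrality d·√n):

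| Pairs | SSS | SDS | Stress defect size |
|---|---|---|---|
| 19 | 70% | 56% | 53% |
| 24 | 80% | 67% | 64% |
| 29 | 88% | 76% | 73% |
| 34 | 92% | 82% | 80% |
| 35 | 93% | 84% | 81% |
| Pairs for 80% power | 24 | 33 | 34 |

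So 24 is the 80% answer for SSS, and 35 is close to the 80% answers for the other two measures. Neither number need be a miscalculation, but each fits a different endpoint and the plan names none.

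With 19 pairs, 80% power needs d = 0.680. That is 2.50 SSS points (2.2 observed), 2.79 SDS points (2.1 observed) or 7.55% LV (5.5 observed). A one-sided 0.05 test with 19 pairs has power 81%, 69% and 67%.

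**4. Citation.** In the reference list, number 2 is the rubidium-82 study and number 8 is the N-13 study. The rubidium-82 differences in the protocol's Table 2 are small and run the other way (SSS 7.2 dipyridamole, 6.6 exercise). Taking those differences at face value and assuming a within-patient correlation of 0.6 to 0.95 (not given), 80% power would need about 118 to 2,546 pairs across the three measures. They cannot be the basis for 24 or 35.

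**The case against.** **The sizing sentence counts subjects, not pairs.** In the Synopsis, 24 is exactly the number of reversible-defect patients enrolled, and the five repeat-Lexiscan subjects may have been meant as a repeatability reference within it. That is possible, but those five supply no Lexercise scan, so they cannot contribute to a Lexercise-versus-Lexiscan difference.

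**Nineteen depends on the allocation.** Enrolment is approximate and only the normal group is capped, so fewer normals and more reversible-defect patients would give more pairs. If patient visit 2 is a mislabelled repeat-Lexiscan visit, some patients might have both research scans. The first reading means enrolling more than the stated 24. The second breaks the count of 37 and the limit of two patient visits. Neither can be excluded until the sections are reconciled, so 19 should be stated as conditional on the Synopsis allocation.

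**The power figures are uncertain.** This stands. With a 95% interval for each standardized effect from 26 patients (SSS 0.18 to 1.01, SDS 0.10 to 0.92, defect size 0.08 to 0.90), power at 19 pairs runs from about 11 to 99%, 7 to 97% and 6 to 96%. The point estimates show what the protocol's own source implies and do not forecast this trial.

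**It is a pilot, and the volunteers may explain the discrepancy.** Since 34 − 10 = 24, Section III may not have been updated when volunteers were added. That is an inference, and it does not explain 35. Pilot status would excuse having no power claim, but this plan makes one.

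**Conclusion.** The concern holds. Three things follow from the text alone: 24 conflicts with 35; the N-13 basis carries the rubidium-82 citation; and Section III's counts do not close and fall below Section VI's number. Under the Synopsis allocation, at most 19 reversible-defect subjects have both scans, five fewer than stated.

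On the assumptions above, going from 24 to 19 pairs raises the chance of missing the prior-study difference from about 20% to 30% for SSS, 33% to 44% for SDS and 36% to 47% for stress defect size. Those figures rest on a test I chose and on effects from exercise versus dipyridamole in 26 patients, which is not the Lexercise-versus-Lexiscan contrast. The inconsistency in the counts does not depend on them. It must be fixed, because the plan's only sizing statement contradicts itself and its allocation does not deliver the smaller number as pairs.

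**What to change.** 1. Use one set of counts in the Synopsis, Section III and Section VI, including the 10 volunteers. Reconcile them with Section V by stating at which visit the 13 repeat-Lexiscan scans take place.
2. If the Synopsis allocation stands, say that the reversible-defect and defect-territory flow comparisons rest on at most 19 subjects with both scans (24 enrolled less 5 returning for repeat Lexiscan), and fewer if Lexiscan is withheld.
3. Name the main defect measure, a paired test, alpha and sidedness, and replace the adequacy claim with the resulting power. For 19 pairs and a two-sided 0.05 paired t-test this is about 70% for SSS, 56% for SDS or 53% for stress defect size. State the source of the effects and their uncertainty. This version is dated September 2016 and enrolment runs from June 2010 to June 2017, so also state whether any outcome data had been examined when the measure was chosen.
4. Cite reference 8 in both sizing sentences. The Background sentence on N-13 exercise PET also cites reference 2 and should be checked.

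**Cost.** Wording only, with no extra patients, if the lower number of pairs is accepted; the price is a less favourable stated power. Keeping 24 pairs alongside five repeat-Lexiscan ischemic subjects would need 24 + 5 = 29 reversible-defect subjects, five more than the Synopsis enrols. Keeping 35 pairs would need 35 + 5 = 40.

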COVER PAGE

NCT #: 01109992

VERSION DATE OF THE DOCUMENT: September 12, 2016

INTEGRATED DUAL EXERCISE AND LEXISCAN PET: IDEAL PET

Version Date: September 12, 2016

Study Type: Single Center Study

Sponsor: Investigator initiated study, PI, [name]

Study Enrollment Period: June 2010 to June 2017

Principal Investigator: [name]

TABLE OF CONTENTS

Topic	Page Number
I. ABBREVIATIONS	3
II. SYNOPSIS	4-7
III. BACKGROUND	8-9
IV. SPECIFIC AIMS	10
V. SIGNIFICANCE	10-11
VI. PRIOR STUDIES	11-14
VII. SUBJECT METHODS AND SELECTION	15-16
VIII. SUBJECT ENROLLMENT	17
IX. STUDY PROCEDURES	18-21
X. BIOSTATISTICAL ANALYSIS	22-23
XI. RISKS AND DISCOMFORT	23-24
XII. POTENTIAL BENEFITS	25
XIII. MONITORING AND QUALITY ASSURANCE	25-26
XIV. REREFENCES	27

ABBREVIATIONS USED:

Myocardial Blood Flow: MBF

Positron Emission Tomography: PET

Computed Tomography: CT

Myocardial perfusion imaging: MPI

Coronary Flow reserve: CFR

Coronary artery disease: CAD

Lexiscan + Exercise: Lexercise

SYNOPSIS

Title of Study: Integrated Dual Exercise And Lexiscan PET: IDEAL PET

Planned Study Period: From 4Q2010 - 2Q2017

Study Objective(s)

Aim 1: To *assess the tolerability and safety* of combined symptom limited exercise stress test with Lexiscan (Lexercise PET) compared to Lexiscan alone (Lexiscan PET).

Aim 2: To *assess the image quality* of Lexercise compared to Lexiscan PET.

Aim 3: To compare *relative and absolute myocardial perfusion imaging* with Lexercise compared to Lexiscan PET to identify CAD.

Planned Total Number of Study Centers and Location

Single study center, Brigham and Women's Hospital, Boston, MA, United States

Design and Methodology

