
Lexiscan PET. However, with PET MPI, imaging is started soon after stress while the subject is still breathing heavy and hence the effects on image quality, both relative PET and dynamic PET images need to be determined. A prior study² from the Ottawa heart institute, evaluated treadmill exercise PET with Rubidium-82. Myocardial uptake of Rubidium-82 was significantly greater with exercise compared with

dipyridamole stress (See Table reproduced from reference²). Higher ratios of myocardial uptake to gut, blood pool, and higher stress myocardial uptake were observed with exercise stress compared with dipyridamole stress. No significant differences in inferior wall defects due to misregistration were noted between exercise and dipyridamole stress studies using a dedicated PET scanner.

Rationale for specific aim 3:

A prior study,² from the Ottawa heart institute, evaluated treadmill exercise PET with Rubidium-82. This study included 50 patients (74% with known CAD and 26% with intermediate to high pretest likelihood of CAD) that underwent both exercise and dipyridamole Rubidium-82 PET within a median of 6 days of each other. More patients preferred exercise stress over dipyridamole. The summed stress (A), rest (B) and difference scores (C) were highly correlated (Figure below reproduced from reference²). Bland-Altman analysis revealed no significant differences in defect size between the treadmill and dipyridamole studies. Also, the agreement between treadmill and dipyridamole studies was similar to the agreement between repeat dipyridamole studies. The authors concluded that treadmill exercise 82Rb PET is feasible and provides imaging results of similar diagnostic content and better quality compared with dipyridamole stress.

In a separate study from the same group, treadmill exercise PET with N-13 ammonia was compared to dipyridamole PET.⁸ This study included 26 patients (41% with prior MI, 35% with prior PCI and 15% with prior CABG) that underwent both exercise and dipyridamole N-13 ammonia PET within a median of 6 days of each other. The summed stress, rest and difference scores were well correlated between the treadmill and dipyridamole studies. The defect size and severity was larger with treadmill exercise compared to dipyridamole PET (See Table below reproduced from reference⁸).

Table 3. Semi-Quantitative and Quantitative Analysis of N-13 PET Myocardial Perfusion Images

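### The Aim 3 sample size is called adequate on a proxy contrast with no quantified bridge; on the synopsis allocation, carrying the whole proxy effect over gives only about 53% to 70% power

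*Combined protocol and SAP*

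**What the plan says.** Aim 3 first compares semi-quantitative defect size, severity and reversibility between the two protocols. In the synopsis (Statistical Plan, Aim 3) the number is justified in one sentence: "Based on the results of one prior study using N-13 ammonia and comparing dipyridamole versus treadmill exercise", "a sample size of 24 subjects with reversible defects should be adequate to identify if significant differences exist between Lexercise and Lexiscan PET protocols". Section VI (Biostatistical Analysis, Aim 3) repeats it with another number: "a sample size of 35 subjects with reversible defects should be adequate to identify if significant differences exist".

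The conditions of this trial are Lexiscan alone and Lexercise. The synopsis defines the latter: "For Lexercise, a symptom limited exercise treadmill study with Lexiscan injection at peak exercise is performed". In the N-13 study, described under the rationale for specific aim 3, "treadmill exercise PET with N-13 ammonia was compared to dipyridamole PET" in 26 patients "that underwent both exercise and dipyridamole N-13 ammonia PET within a median of 6 days of each other". It was therefore a paired study of exercise alone against a different vasodilator.

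For Aim 3 the plan states no sizing endpoint, target difference, standard deviation, test, alpha or power.

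**The concern.** Neither condition of the sizing study is a condition of this trial. The prior study replaced one stressor with another, whereas this trial adds exercise to a vasodilator that is present in both sessions. The size of the difference in the trial's own contrast is unknown, and the plan does not say what share of the prior effect it expects to see.

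The adequacy statement also counts subjects with reversible defects, while the comparison needs subjects who have both a Lexiscan and a Lexercise scan. These are not the same number.

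At stake is how a non-significant Aim 3 result is read. A size declared adequate in advance invites the reader to take it as evidence that the protocols perform alike.

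**Working it through.** **Inputs.** Table 3 of the rationale for specific aim 3 (exercise, dipyridamole, correlation):

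- Summed stress score (SSS): 9.1 ± 5.7, 6.9 ± 5.9, r = 0.80
- Summed difference score (SDS): 5.8 ± 4.7, 3.7 ± 4.6, r = 0.61
- Stress defect size, % of left ventricle: 19.3 ± 11.5, 13.8 ± 13.6, r = 0.62

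Assumed, because not stated: paired t-test, two-sided 0.05, 80% target power, and the same paired SD in this trial.

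**Paired SD and standardised effect.** SD of the difference = √(s1² + s2² − 2·r·s1·s2); effect d = mean difference / SD.

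- SSS: √(32.49 + 34.81 − 53.81) = 3.67; d = 2.2/3.67 = 0.60
- SDS: √(22.09 + 21.16 − 26.38) = 4.11; d = 2.1/4.11 = 0.51
- Defect size: √(132.25 + 184.96 − 193.94) = 11.10; d = 5.5/11.10 = 0.50

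Check against the table, taking all 26 patients in each row: t = d·√26 = 3.05, 2.61 and 2.53, so p = 0.005, 0.015 and 0.018. These agree with the printed <0.01, <0.02 and <0.02.

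**The plan's own figure.** It cannot be derived from stated inputs. With the whole effect carried over, the noncentral t (n − 1 degrees of freedom, noncentrality d·√n) gives N = 24 for SSS, 33 for SDS and 34 for defect size at 80% power. So 24 fits SSS, and 35 is close to what the other two need.

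**Number of pairs.** The synopsis enrols 24 patients with reversible defects and sends 5 ischemic subjects to repeat Lexiscan: 24 − 5 = 19. The total agrees: 19 ischemic + 8 normal (16 − 8) + 10 volunteers = 37, the synopsis figure for Lexercise. Section III instead has 34 with reversible defects, so 34 − 5 = 29 pairs; but its 34 Lexercise subjects plus 13 repeats make 47, not 50.

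**Power (%) with the whole effect carried over**

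| Pairs | SSS | SDS | Defect size |
|---|---|---|---|
| 19 (synopsis allocation) | 69.5 | 55.9 | 53.3 |
| 24 (synopsis number, all paired) | 80.2 | 67.0 | 64.2 |
| 29 (Section III allocation) | 87.6 | 75.7 | 73.1 |
| 35 (Section VI number, all paired) | 93.1 | 83.6 | 81.2 |

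**Power (%) at 19 pairs by share of the prior effect (shares are assumptions)**

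| Share | SSS | SDS | Defect size |
|---|---|---|---|
| 50% | 23.5 | 18.4 | 17.6 |
| 75% | 45.8 | 35.3 | 33.5 |
| 100% | 69.5 | 55.9 | 53.3 |
| 125% | 87.0 | 75.0 | 72.3 |

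**Precision at 19 pairs.** The 95% half-width is 2.101·SD/√19: 1.8 for SSS, 2.0 for SDS and 5.4 percentage points for defect size, against prior differences of 2.2, 2.1 and 5.5.

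**The case against.** Four points have weight.

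- The number 24 has a basis. SSS is the plan's own measure of total abnormal myocardium (interpretation of relative images, Section V), and 24 pairs give 80% power for it at full transfer. This stands: a reader might infer that 24 is wrong even on its own terms, and the documents do not support that.
- Proxy data are normal here. The document calls the study a pilot and says the combined protocol has not been used with PET. It also frames the comparison by class, exercise plus vasodilator against vasodilator, which makes dipyridamole a reasonable stand-in for Lexiscan. This stands too: using the N-13 study is not the fault.
- The Background does offer a bridge. Exercise constricts diseased vessels, and a vasodilator added at peak exercise mainly dilates normal ones, so contrast may improve. This argues for an effect above the proxy, which is why the range must run past 100%. But it is qualitative and fixes no difference to size for.
- No passage plans to conclude that the protocols are equal. Hypothesis 3 is directional and Aim 3 sets no P threshold. The misreading is a risk that the wording invites, not a planned analysis.

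A reader might also infer that the effect must be smaller than the proxy, because Section V gives regadenoson after the treadmill stops and both compared images are then vasodilator images. No passage says that this narrows the difference, and the Background argues the reverse. Nor does the Rubidium-82 study of the same two stressors settle it. It found no significant difference (SSS 6.6 with exercise, 7.2 with dipyridamole), and this trial allows that tracer, but it too is a proxy. The direction of the departure is unknown.

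**Conclusion.** The concern holds in a limited form. The adequacy statement rests on a proxy contrast without a quantified link to the trial's own contrast. On the synopsis allocation, power reaches 80% for none of the three measures even if the whole proxy effect carries over: about 70% for SSS, 56% for SDS and 53% for defect size. The number 24 reaches 80% only for SSS, an endpoint the sizing sentence does not name, and only if all 24 patients contribute a Lexercise-Lexiscan pair, which the synopsis rules out.

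This rests on a paired t-test at two-sided 0.05, the paired SDs derived from Table 3, the synopsis split, and no loss of pairs. The plan makes no allowance for loss, although it withholds Lexiscan after certain treadmill findings. On the Section III allocation (29 pairs), SSS would pass 80% at full transfer, while SDS and defect size would not. The share of the effect that transfers cannot be found in the documents.

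**What to change.** In the synopsis and in Section VI, Aim 3:

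1. Replace the adequacy claim with a statement that the prior N-13 study compared exercise alone with dipyridamole and is indicative only.
2. Reconcile 24 with 35, and state the planned number of ischemic Lexercise-Lexiscan pairs (19 on the synopsis allocation).
3. Give power at that number for SSS, SDS and defect size over a range of transfer on both sides of 100%, for example 50% to 125%, with the test and alpha named.
4. Report Aim 3 as a paired mean difference with a 95% confidence interval, and draw no conclusion of no difference from P > 0.05.

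The cost is protocol wording only, with no extra patients and no change in the data collected. The drawback is a less favourable stated justification for the sample size.
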